6.6 Analyses

6.6.1 Primary Analyses

The result for each test will be compared with the ASIS for that anatomic site and organism. For each diagnostic test, PPA and NPA will be estimated using 95% Score confidence intervals. Confidence intervals will be estimated using the Score method.³⁴

In the primary analysis, we will follow the FDA guidance document for incorporating indeterminate ASIS or test results for the test under consideration that are equivocal.³⁴ Indeterminate ASIS results will be counted against the results for the test under consideration, as described in Tables 4 and 5. Tables 4 and 5 will be presented in the analysis report, showing all combinations of Infected/Indeterminate/Not Infected with all outcomes from the test under consideration (Positive/Equivocal/Negative/No result or Invalid)

If the test under consideration has “no result” because the test was not run and no attempt was made to test the sample, it will be excluded from the primary analysis.

Table 4. Use of the ASIS in calculation of the positive and negative percent agreement for the Company 2 Assay (Company 2) and Company 3 Assay (CT only).

| | ASIS | | |
|--|----------|----------------|--------------|
| | Infected | Indeterminate* | Not infected |
| | | | |

| | | | | |
|---|-----------|-----------------------|---|-----------------------|
| Result of Test under Consideration** | Positive | A | D | G |
| | Equivocal | B | E | H |
| | Negative | C | F | I |
| | No result | Exclude from analysis | | |
| | PPA | $A / (A+B+C+F)$ | | |
| | NPA | | | $I / (G + H + I + D)$ |

*The middle, indeterminate column will be included in the analyses as “Infected” or “Not infected” as described in the sensitivity analyses below.

**Per the ASIS definition in Section 2.3

Comprehensive sensitivity analyses will be conducted considering multiple scenarios. These include:

- Classify indeterminate tests on the basis of symptom status. Include indeterminate tests as infected if the participant is symptomatic in that compartment. Include indeterminate tests as not infected in the participant is asymptomatic in that compartment.
- Include all indeterminate tests as infected.
 - $PPA = (A+D) / (A+B+C+D+E+F)$
 - $NPA = I / (G+H+I)$
- Include all indeterminate tests as not infected.
 - $PPA = A / (A+B+C)$
 - $NPA = (F+I) / (D+E+F+G+H+I)$
- Considering indeterminate and equivocal test results as “missing”, with the assumption of missing at random, and model the missing results.

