- Additional sensitivity analyses, including the use of latent class models, will be explored. Details will be in the statistical analysis plan.

Table 5. Use of the ASIS in calculation of the positive and negative percent agreement for the Company 1 Assay (Company 1) and Company 3 Assay (NG only).

| | | ASIS | | |
|---|-----------------------|-----------------------|----------------|---------------|
| | | Infected | Indeterminate* | Not infected |
| Result of Test under Consideration** | Positive/Detected | A | C | E |
| | Negative/Not detected | B | D | F |
| | No result | Exclude from analysis | | |
| | PPA | $A / (A+B+D)$ | | |
| | NPA | | | $F / (C+E+F)$ |

*The middle, indeterminate column will be included in the analyses as “Infected” or “Not infected” as described in the sensitivity analyses below.

**Per the ASIS definition in Section 2.3

If the test under consideration has “no result” because the test was not run and no attempt was made to test the sample or because of invalid ASIS results it will be excluded from the primary analysis.

Comprehensive sensitivity analyses will be conducted. These include:

- Classify indeterminate tests on the basis of symptom status. Include indeterminate tests as Infected if the participant is symptomatic in that compartment. Include indeterminate tests as not infected in the participant is asymptomatic in that compartment.

- Include all indeterminate tests as infected
 - $PPA = (A+C) / (A+B+C+D)$
 - $NPA = F / (E+F)$
- Include all indeterminate tests as not infected
 - $PPA = A / (A+B)$
 - $NPA = (D+F) / (C+D+E+F)$
- Additional sensitivity analyses that consider indeterminate results as “missing” and utilize imputation strategies, and graphical techniques
- Additional sensitivity analyses, including the use of latent class models, will be explored. Details will be in the statistical analysis plan.

There are pros and cons to the manner in which indeterminates are handled and the resulting calculations of PPA and NPA. The primary definition is the most conservative but is biased downwards. If $PPA > 90\%$ under this scenario, then the conclusion of $PPA > 90\%$ is clear. The second and third sensitivity analyses count indeterminates (treat all as infected or not infected, respectively) but may not be conservative for calculations of PPA and NPA.

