For all final analyses, data collected from eCRFs or data entered by the laboratories in the laboratory information management system (LIMS) will be used. The primary analysis will evaluate the result for each diagnostic test (i.e., test under consideration) and compare with the ASIS for each anatomic site and organism combination. For each diagnostic test, positive percent agreement (PPA) and negative percent agreement (NPA) will be estimated using 95% confidence intervals. Confidence intervals will be estimated using the Score method. The primary analysis will also follow FDA guidance for incorporating indeterminate ASIS or test results for the test under consideration that are equivocal. As a result, all combinations of Infected/Indeterminate/Not Infected with all outcomes from the test under consideration (Positive/Equivocal/Negative/No result or Invalid) will be presented. If the test under consideration has "no result" because the test was not run and no attempt was made to test the sample, it will be excluded from the primary analysis.

Sensitivity analyses associated with the primary analyses will be conducted to examine the impact of different classifications of indeterminate results (i.e., all infected, all not infected, account for symptom status). Additional subgroup and secondary analyses are planned.

E. Report Distribution List

Unless otherwise mentioned, distribution lists for monitoring and analysis reports are comprised of:

Protocol Team: [contact] members

Core Team: Protocol Chair, Protocol Clinician, Project Lead, Statisticians, Data Management, Clinical Trials Manager, Clinical Research Associate, Regulatory Associate.

DMID: DMID representative

DIR: Designated Independent Reviewer

Table 2: Report Distribution Summary

Tuble 2. Report Distribution e	Janniary	
Report	Frequency	Distribution List
Harvard Monitoring Report	Bi-monthly (or as determined by core team)	Core Team
Open Administrative Interim Report	Every 3 months or every 500 participants (whichever comes first)	DIR, Core Team, DMID
Closed Administrative Interim Report	Every 3 months or every 500 participants (whichever comes first)	DIR, Statisticians
Final Analysis Report	End of study per study timeline	Protocol Team

F. Application Validation

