 - Table 11 and Table 12: Company 2 Assay (Company 2) and Company 3 Assay (Company 3).
 - Table 13 and Table 14: Company 1 Assay (Company 1) and Company 3 Assay (Company 3).
- h. Figure: Plot of PPA and 95% confidence interval band versus proportion of indeterminate ASIS results assumed to be positive (range of 0 to 1); vice-versa for NPA plot.
- i. Table: Using Fischer's exact test, the association between test results and randomized swab order will be examined. Associations will be conducted by anatomical site and organism combination.

Table 11: Result of Test under Consideration versus ASIS: Company 2 Assay (Company 2) and Company 3 Assay (Company 3)

		ASIS			
		Infected	Indeterminate	Not infected	
	Positive	A	D	G	
Result of Test under Consideration	Equivocal	В	E	Н	
	Negative	С	F	I	
	No result	Exclude from analysis ¹			
¹ Note: If the test under consideration has "no result" because the test was not run and no attempt was made to test the sample, the					

test result will be excluded from primary analysis. If the ASIS result is invalid, this result will be excluded from the primary analysis.

Table 12: Calculation of the positive and negative percent agreement: Company 2 Assay (Company 2) and Company 3 Assay (Company 3)

Analysis Type	PPA	NPA		
Primary Analysis	A / (A+B+C +F)	l / (G+H+l + D)		
Sensitivity Analysis Scenarios				
Classify indeterminates ¹ using symptom status reported	A / (A+B+C+F)	I / (G+H+I+D)		
from [SIGNS AND SYMPTOMS]				
Include all indeterminate tests as infected.	(A+D) / (A+B+C+D+E+F)	l / (G+H+I)		
Include all indeterminate tests as not infected.	A / (A+B+C)	(I+F) / (D+E+F+G+H+I)		
Consider indeterminate and equivocal test results as "missing", with the assumption of missing at random, and model the missing results. ²	A / (A+C)	l / (G+l)		
Classify indeterminate tests on the basis of symptom status. Include indeterminate tests as Infected if the participant is symptomatic in that compartment; include indeterminate tests as not infected in the participant is asymptomatic in that compartment. Cells B, D, E, F and H will be assigned or weighted to cells A, C, G and I based on modeling of the missing results.				

Table 13: Result of Test under Consideration versus ASIS: Company 1 Assay (Company 1) and Company 3 Assay (Company 3)

		ASIS			
		Infected	Indeterminate	Not infected	
	Positive/Detected	A	С	E	
Result of Test under Consideration	Negative/Not detected	В	D	F	
	No result	Exclude from analysis ¹			

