Note: If the test under consideration has "no result" because the test was not run and no attempt was made to test the sample, the					

¹ Note: If the test under consideration has "no result" because the test was not run and no attempt was made to test the sample, the test result will be excluded from primary analysis. If the ASIS result is invalid, this result will be excluded from the primary analysis.

Table 14: Calculation of the positive and negative percent agreement: Company 1 Assay (Company 1) and for the Company 3 Assay (Company 3)

Analysis Type	PPA	NPA
Primary Analysis	A / (A+B +D)	F / (C+E +F)
Sensitivity Analysis Scenarios		
Classify indeterminates ¹ using symptom status reported from [SIGNS AND SYMPTOMS]	A / (A+B+D)	F / (C+E+F)
Include all indeterminate tests as infected.	(A+C) / (A+B+C+D)	F / (E+F)
Include all indeterminate tests as not infected.	A / (A+B)	(D+F) / (C+D+E+F)
Consider indeterminate and equivocal test results as "missing", with the assumption of missing at random, and model the missing results. ²	A / (A+B)	F / (E+F)

¹ Classify indeterminate tests on the basis of symptom status. Include indeterminate tests as Infected if the participant is symptomatic in that compartment; include indeterminate tests as not infected in the participant is asymptomatic in that compartment.
² Cells C and D will be assigned or weighted to cells A, B, E and F based on modeling of the missing results.

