5.4.4. Secondary (Global) Analyses

Note: Analysis programs may require independent results verification per CBAR PROG.10033.

The following will be conducted for the three diagnostic tests.

- a. Table: Summary of estimated positive and negative predictive values (PPV and NPV).
- b. Figure: Plot of predictive PPV and NPV estimates as a function of prevalence for each test (point estimates and 95% pointwise confidence bands)
- c. Table/Figure: The 95% Score confidence interval estimates of positive and negative likelihood ratios with forest plot display (one plot per test).
- d. Table/Figure: Sensitivity analyses estimating PPV, NPV, and positive and negative likelihood ratios where indeterminates are: a) counted as all infected, b) all not infected, and c) based on symptom status reported in [SIGNS and SYMPTOMS].

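### SAP Tables 12 and 14 print the primary formulas in the symptom-status sensitivity row, contradicting the row's own footnote and protocol 6.6.1

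*SAP*

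**What the plan says.** SAP section 5.4.3 cross-classifies each test against the anatomic site infection status (ASIS).

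- **Table 11** (assays with an equivocal result): A, B, C are positive, equivocal and negative results at infected sites; D, E, F are the same at indeterminate sites; G, H, I are the same at not-infected sites.
- **Table 13** (assays without an equivocal result): A, B are infected, C, D indeterminate, and E, F not infected.

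Tables 12 and 14 then give PPA and NPA formulas for the primary analysis and for several sensitivity analyses. One of these classifies indeterminates by reported symptoms. Its footnote says: "Include indeterminate tests as Infected if the participant is symptomatic in that compartment; include indeterminate tests as not infected" when the participant is asymptomatic at that site. Protocol 6.6.1 has the same rule in words for both groups of assays, for example "Include indeterminate tests as infected if the participant is symptomatic in that compartment". It prints no formula for it.

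SAP section D, Final Analysis Considerations, says the sensitivity analyses are there to "examine the impact of different classifications of indeterminate results (i.e., all infected, all not infected, account for symptom status"). Section 5.4.4(d) carries the same classification over to predictive values and likelihood ratios, "based on symptom status reported in [SIGNS and SYMPTOMS"], also without a formula.

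**The concern.** The symptom-status row should move each indeterminate site to the infected or the not-infected column, depending on symptoms. Its printed formulas have no term that depends on symptoms and match the primary row exactly, apart from spacing. The primary row does something different: it counts indeterminates against the test, with indeterminate negatives in the PPA denominator and indeterminate positives in the NPA denominator.

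If the row is programmed as printed, the report will show a symptom-based sensitivity analysis that agrees perfectly with the primary analysis. That agreement could be read as robustness when it only reflects the same formula computed twice. The error would repeat in the subgroup analyses, because section 5.4.5 reruns section 5.4.3 in each subgroup.

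**Working it through.** **1. Printed rows side by side**

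| | Primary row | Symptom-status row |
|---|---|---|
| Table 12 PPA | A/(A+B+C+F) | A/(A+B+C+F) |
| Table 12 NPA | I/(G+H+I+D) | I/(G+H+I+D) |
| Table 14 PPA | A/(A+B+D) | A/(A+B+D) |
| Table 14 NPA | F/(C+E+F) | F/(C+E+F) |

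**2. What the footnote rule gives.** Split each indeterminate cell into symptomatic (s) and asymptomatic (a) parts. Move s to infected and a to not infected.

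- Table 12: PPA = (A+Ds)/(A+B+C+Ds+Es+Fs); NPA = (I+Fa)/(G+H+I+Da+Ea+Fa)
- Table 14: PPA = (A+Cs)/(A+B+Cs+Ds); NPA = (F+Da)/(E+F+Ca+Da)

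**3. A check that needs no counts.** Section 5.4.5 repeats the analyses separately in symptomatic and asymptomatic participants.

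- Symptomatic subgroup: every indeterminate is symptomatic, so the footnote rule must reproduce the all-infected row. In Table 12 that is (A+D)/(A+B+C+D+E+F) for PPA.
- Asymptomatic subgroup: it must reproduce the all-not-infected row, A/(A+B+C).

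The step 2 formulas meet both limits. The printed row gives A/(A+B+C+F) in both subgroups and in general meets neither.

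**4. When the printed row happens to be right.** In Table 14, PPA rises with Cs and falls with Ds. Its minimum is at Cs = 0 and Ds = D, which is the printed formula; NPA has its minimum at the same split. So the printed Table 14 row equals the footnote rule only in the worst case for the test. In Table 12, cell E can also enter the PPA denominator, so the footnote rule can fall on either side of the printed value.

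**5. Size, Table 12.** All counts are assumed: A=190, B=1, C=5, D=3, E=2, F=6, G=15, H=4, I=2607. The 95% Score lower bound is taken as the Wilson bound, [p + z²/2n − z√(p(1−p)/n + z²/4n²)]/(1 + z²/n) with z = 1.96.

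- Printed PPA: 190/(190+1+5+6) = 190/202 = 94.1%. Lower bound: (0.9406 + 0.0095 − 0.0340)/1.0190 = 89.9%.
- Footnote rule over all 4 × 3 × 7 = 84 possible splits:
  - lowest 190/204 = 93.1%, lower bound 88.8% (Ds=0, Es=2, Fs=6)
  - highest 193/199 = 97.0%, lower bound 93.6% (Ds=3, Es=0, Fs=0)
  - one intermediate split (Ds=2, Es=1, Fs=1): 192/200 = 96.0%, lower bound 92.3%
- Against the printed PPA, the footnote rule is higher in 69 splits, equal in 3 and lower in 12. Its lower bound exceeds 90% in 66 and falls short in 18. These are counts of possible splits, not probabilities.
- NPA: printed 2607/2629 = 99.16%; footnote rule 2607/2631 = 99.09% to 2613/2632 = 99.28%.

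**6. Size, Table 14.** Assumed A=190, B=6, C=3, D=6. Printed PPA is 190/202 = 94.1%, lower bound 89.9%. The footnote rule gives 94.1% to 193/199 = 97.0%, with the lower bound above 90% in 26 of 4 × 7 = 28 splits.

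**7. Dependence on the number of indeterminates** (Table 12)

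| Assumed A/B/C | D/E/F | Printed PPA | Footnote rule |
|---|---|---|---|
| 190/1/5 | 1/0/1 | 190/197 = 96.4% | 96.4% to 97.0% |
| 190/1/5 | 1/1/2 | 190/198 = 96.0% | 95.5% to 97.0% |
| 190/1/5 | 3/2/6 | 190/202 = 94.1% | 93.1% to 97.0% |
| 151/1/5 | 10/2/10 | 151/167 = 90.4% | 151/157 = 96.2% (all asymptomatic); 161/179 = 89.9% (all symptomatic) |

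In the first two rows every lower bound stays above 90%, so the reading against 90% does not change.

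**The case against.** The strongest defence is that the letters in this row mean cells recounted after reclassification. The missing-at-random row does work that way: its Table 12 footnote says "Cells B, D, E, F and H will be assigned or weighted to cells A, C, G and I". On that reading the indeterminate column is empty, the extra terms are zero, and the estimate is correct.

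This does not rescue the row. The missing-at-random row says that cells are reassigned and drops the moved cells, printing A/(A+C) and I/(G+I). The symptom row has no such statement and keeps F and D (D and C in Table 14). The all-infected and all-not-infected rows in the same tables use the original cells. At best the row carries terms with no meaning.

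Other points go to weight, and most of them stand:

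- The rule is clear in words in the row label, the footnotes and the protocol, and section 5.4.3 requires independent verification of the programs, so a programmer may well do the right thing. But the SOP appended to the SAP defines validation as conformity to the analysis specifications, and here the printed specification is the faulty part.
- No decision rests on this row. The 90% reading is tied to the primary definition, and the other indeterminate rows and the plot in item h still show how much indeterminates matter.
- The size depends on how many indeterminates occur. The 11-indeterminate example puts the printed bound just under 90%; with few indeterminates the effect is small.

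**Conclusion.** The inconsistency is real and follows from the printed text alone. In the letters of Tables 11 and 13, the symptom-status row returns the primary PPA and NPA for any data and does not perform the analysis that its footnote and protocol 6.6.1 describe.

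The primary estimates and the sample size are not affected. The loss is confined to the symptom-based sensitivity estimates and their repeats in the subgroups. Their size is unknown, because the documents give no counts. Under the assumed counts the PPA difference runs from under one percentage point with two indeterminates to 2.9 points with 11 (97.0% against 94.1%), and to 5.8 points with 22 (96.2% against 90.4%). The reading of the lower bound against 90% can change when there are enough indeterminates. In the NPA example the movement is only about 0.1 point. This should be corrected before the analysis programs are finalised, but it does not threaten the main conclusions.

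**What to change.** Replace the symptom-status row in Tables 12 and 14 in one of two ways, which give the same result:

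- **Split-cell form**, with s and a defined in the footnote as symptomatic and asymptomatic at that anatomic site:
  - Table 12: PPA = (A+Ds)/(A+B+C+Ds+Es+Fs); NPA = (I+Fa)/(G+H+I+Da+Ea+Fa)
  - Table 14: PPA = (A+Cs)/(A+B+Cs+Ds); NPA = (F+Da)/(E+F+Ca+Da)
- **Recounted form**: state that the cells are recounted after reclassification, and print A/(A+B+C) and I/(G+H+I) in Table 12, and A/(A+B) and F/(E+F) in Table 14, with no indeterminate letters.

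Two small additions would complete the definition: say how an indeterminate site with missing symptom status is assigned, and have item c) of section 5.4.4(d) refer to the same definition.

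The cost is SAP wording and one row in each of two tables. Site-specific symptoms are already collected (SAP section 1.2, Study Population Characteristics), so no new data are needed.

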6.3 Sample Size

For each assay, PPA and NPA³⁵ will be estimated for each of three diagnostic tests defined by pathogen - anatomical site combinations:

- *Neisseria gonorrhoeae* in the rectum
- *Neisseria gonorrhoeae* in the pharynx
- *Chlamydia trachomatis* in the rectum
- *Chlamydia trachomatis* in the pharynx

Each pathogen/anatomic site combination will be evaluated by constructing 95% Score confidence interval estimates for PPA and NPA and evaluating whether 90% can be ruled out by the lower bound of the CI with reasonable confidence.

NPA is expected to be greater than PPA and there will be considerably more not-infected than infected anatomic site, implying that there will be greater power for evaluating NPA. Thus it will suffice to size the study to evaluate PPA.

Assuming that the true PPA is 96%,¹³ then 157, 174, and 196 evaluable participants that are infected are needed to have 80%, 85%, and 90% power respectively to demonstrate a PPA of greater than 90%. Since all of the participants will contribute to the evaluation of all three pathogen-anatomical site diagnostic tests, it will suffice to size the study for the diagnostic test with the lowest expected prevalence (except CT in the pharynx). The study will be more than sufficiently sized for more prevalent disease.

It is expected that the disease prevalence of NG in the rectum, NG in the pharynx, and CT in the rectum will each be greater than 7.5% in the population under evaluation.^{13,14,16-20} Table 3 summarizes the required number of participants to have 80% and 90% probabilities of obtaining the 157, 174, and 196 evaluable participants that are disease-positive to have 80%, 85%, and 90% power when the true prevalence of disease is 7.5%, 10%, and 12.5%.

Table 3: Sample size required number to have 80% and 90% probabilities of obtaining the 157, 174, and 196 evaluable participants that are disease-positive when the true prevalence of disease is 7.5%, 10%, and 12.5% in order to have 80%, 85%, and 90% power (two-sided alpha=0.05) to conclude that sensitivity is greater than 90% when the true sensitivity is 96%.

| Prevalence of Disease Positive | Power | Required Disease Positive to Obtain Power | Required Sample Size to have 80% probability of obtaining required Disease positive participants | Required Sample Size to have 90% probability of obtaining required Disease positive participants |
|--------------------------------|-------|---|--|--|
| 7.5% | 80% | 157 | 2250 | 2325 |

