5.4.2. Final Analysis Considerations

Note: All dataset derivation programs for this endpoint will undergo independent results verification in accordance with CBAR PROG.10033; validation requirements for analysis programs are stated below.

As noted previously, for all final analyses, data collected from eCRFs or data entered by the laboratories in the laboratory information management system (LIMS) will be used. Data from additional sources such as machine data or issue tracking logs may be reviewed for clarification, but will not be used for analysis.

The result for each diagnostic test will be compared with the ASIS for that anatomic site and organism. PPA and NPA will also be estimated for each diagnostic test with 95% confidence intervals. Confidence intervals will be estimated using the Score method.⁸ If the test under consideration has "no result" because the test was not run and no attempt was made to test the sample, the test result will be excluded from primary analysis. If the ASIS result is invalid, this result will be excluded from the primary analysis.

FDA guidance documents will be followed as part of the primary analysis to incorporate indeterminate ASIS or test results for the test under consideration that are equivocal.⁹ It is recognized that there are pros and cons to the manner in which indeterminates are handled and how these impact the resulting estimates of PPA and NPA. The primary analysis approach is the most conservative and is biased downwards. If PPA is >90% under this scenario, then the conclusion of PPA >90% is clear.

Sensitivity analyses will be conducted as appropriate to evaluate the impact of diagnostic accuracy for a range of scenarios addressing indeterminate ASIS results. This will include counting indeterminate ASIS results against the results for the test under consideration with all combinations of Infected/Indeterminate/Not Infected with all outcomes from the test under consideration (Positive/Equivocal/Negative/No result or Invalid) evaluated. These analyses may not be conservative for calculations of PPA and NPA.

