5.4.3. Primary Analyses

The following will be conducted for the three diagnostic tests.

Note: Analysis programs will require independent results verification per CBAR PROG.10033.

 Table: For each diagnostic assay (including the tiebreaker assay), frequency of observed test outcomes by anatomical site and organism combination. [See Table 8 described in Section 5.3.2; data source: LAB DATA]

⁸ FDA. Establishing the performance characteristics of in vivo diagnostics devices for Chlamydia trachomatis and/or Neisseria gonorrhoeae: screening and diagnostic testing. (2011).

⁹ FDA. Establishing the performance characteristics of in vivo diagnostics devices for Chlamydia trachomatis and/or Neisseria gonorrhoeae: screening and diagnostic testing. (2011).

- b. Table: Frequency (%) of re-tests by clinic and platform. This will be conducted for each test under consideration and be presented by anatomical site and organism combination. [Data source: LAB DATA; DEMOG]
- c. Table: Listing and frequency (%) of re-tests results by platform. This will be conducted for each test under consideration and be presented by anatomical site and organism combination. [Data source: LAB DATA]
- d. Table/Figure: Frequency of comparator NAAT result and tiebreaker result combinations to define ASIS. This will be conducted for each test under consideration and be presented by anatomical site and organism combination. There will be a total of three tables to reflect the three tests under consideration. [See **Table 9** previously described in in Section 5.3.2; data source: LAB DATA]
- e. Table/Figure: Number (%) of observed total test results, ASIS results, and prevalence (i.e., infection) rate. This will be conducted for each test under consideration and be presented by anatomical site and organism combination. [See **Table 10** previously described in Section 5.3.2; data source: LAB DATA]
- f. Table: Observed infection rate by clinic. This will be conducted for each test under consideration and be presented by anatomical site and organism combination. [Data source: LAB DATA; DEMOG]
- g. Tables:
 - Cross comparison of number (%) of results of test under consideration versus ASIS;
 - Estimates of PPA and NPA with 95% Score confidence intervals;
 - Due to differences in PPA and NPA calculations for NAAT platforms that do not have an [redacted] result when it is the test under consideration, analysis results will be estimated and presented separately based on this distinction as follows:

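### The missing-at-random sensitivity row of SAP Tables 12 and 14 has no interval method of its own, and the Score interval it inherits would treat modelled results as observed

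*SAP*

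**What the plan says.** SAP 5.4.3 lists four sensitivity scenarios beneath the primary analysis in Tables 12 and 14. The last assumes that indeterminate and equivocal results are missing at random and models them. Footnote 2 says how the cells are completed.

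- Table 12 (Company 2, and Company 3 for CT): "Cells B, D, E, F and H will be assigned or weighted to cells A, C, G and I based on modeling". The row's formulas are PPA = A/(A+C) and NPA = I/(G+I).
- Table 14 (Company 1, and Company 3 for NG): "Cells C and D will be assigned or weighted to cells A, B, E and F based on modeling of the missing results". The row's formulas are PPA = A/(A+B) and NPA = F/(E+F).

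Item g of SAP 5.4.3, which introduces these tables, asks for "Estimates of PPA and NPA with 95% Score confidence intervals". SAP 5.4.2 gives the general rule: "Confidence intervals will be estimated using the Score method". Neither makes an exception for the modelled row.

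For the Table 5 assays, Protocol 6.6.1 adds only this: "Additional sensitivity analyses that consider indeterminate results as “missing” and utilize imputation strategies, and graphical techniques". Neither document gives the model, its covariates, a number of imputations or a variance method. Neither gives an expected rate of indeterminate or equivocal results.

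**The concern.** A Score interval is built for an observed binomial count. After the cells are completed, part of the count comes from a model. Weighting produces fractional pseudo-counts. Assignment counts a random draw as if it had been seen. In both cases the denominator is restored to full size, so the interval has the width of a study with nothing missing. Uncertainty in the fitted model is ignored, and with a single assignment so is the noise of the draw.

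A row that treats results as missing should show the loss of information, and this one would not. The PPA denominator is small, so few modelled results matter: with 3,000 − 167 = 2,833 participants and 7.5% prevalence there are about 212 infected sites, and about 21 modelled results make up 10% of them. SAP 5.4.5 repeats the analysis by sex and by symptom status, where fewer still are needed to reach that share.

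There is also a practical side. SAP 5.4.3 requires independent verification of these programs. Two programmers who follow the text have only the Score method to apply.

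**Working it through.** **The plan's own figure.** Protocol 6.3 states "157, 174, and 196 evaluable participants that are infected are needed to have 80%, 85%, and 90% power respectively", for a null PPA of 90%, a true PPA of 96% and two-sided alpha 0.05. The one-sample score formula is n = [(z₀.₉₇₅√(p₀q₀) + z_power√(p₁q₁))/(p₁−p₀)]². For 80% power this is [(1.960×0.300 + 0.842×0.196)/0.06]² = 157.5. For 85% and 90% power it gives 173.8 and 195.6. The plan's figures reproduce. It has no figure for the modelled row.

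**Width.** Take 157 infected sites and PPA 96%, with test results missing completely at random and no informative covariates (assumptions). The Score limits are [p + z²/2n ± z√(pq/n + z²/4n²)]/(1 + z²/n).

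- Completed count, n = 157: (0.9722 ± 0.0330)/1.0245, or 91.7–98.1%, whatever share was filled in.
- Observed only, 10% missing, n = 141: (0.9736 ± 0.0351)/1.0272, or 91.4–98.2%.

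The ratio of completed to observed-only width is 0.99 at 2% missing, 0.97 at 5%, 0.94 at 10% and 0.89 at 20%.

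**Coverage.** The simulations generate a table of ASIS by test result with prevalence 7.5% (Protocol 6.3), PPA 96% and an assumed NPA of 99%. Results are missing completely at random. Cells are completed by one random assignment or by model weights, and a Score interval is put on the completed counts. Coverage of PPA by the nominal 95% interval, assigned / weighted:

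| Indeterminate + equivocal (assumed) | N = 2,833 | N = 3,000 |
|---|---|---|
| 1% + 1% | 95.0 / 95.1 | 95.2 / 95.6 |
| 5% + 5% | 93.2 / 93.9 | 93.0 / 93.9 |
| 10% + 10% | 91.2 / 92.6 | 90.3 / 93.1 |

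The N = 3,000 column used 2,500 replicates and carries about ±1 point of simulation error. The complete-case Score interval at N = 2,833 covers 95.2–95.4%.

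At a true PPA of 90%, the chance that the lower limit exceeds 90% is 1.8% for complete cases. With single assignment it is 2.8% when 10% of the PPA denominator is modelled and 4.1% when 19% is modelled. The nominal level is 2.5% per side.

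**How large the modelled share may be.** Protocol Table 2 makes an ASIS indeterminate mainly when one positive, one negative and one equivocal or no-result occur together. Assume independent errors, sensitivity 96%, specificity 99%, and final rates after repeat of 1% equivocal and 1% no result per assay. At an infected site the probabilities of a positive and a negative are 0.98×0.96 = 0.9408 and 0.98×0.04 = 0.0392. The indeterminate share is then about 6×0.9408×0.0392×0.02 = 0.0044, or 0.4%. With 5% and 5% it is 6×0.864×0.036×0.10 = 0.0187. Patterns with no definite result add under 0.001, giving about 1.9%.

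Table 14 models only these indeterminate results, so its modelled share would be about 0.4–1.9% of infected sites. For Table 12 to reach 10–19%, final equivocals would have to supply roughly 8–17% (10 − 1.9 and 19 − 1.9).

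**The case against.** The strongest reply is that the SAP does not say how the interval for this row is computed. Item g is one bullet covering several tables. The row's cells hold point-estimate formulas, footnote 2 leaves the model open, and the protocol's mention of imputation does not commit to a single fill-in. This stands in part. A reader might infer that the SAP states that a Score interval is put on completed counts; it implies this, because no other method is offered, but does not say so.

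The second reply is that little depends on the row. A reader might infer that the study's 90% conclusion rests on it. The documents place that conclusion on the primary definition, which Protocol 6.6.1 and SAP 5.4.2 call the most conservative. SAP Section D lists three ways of classifying indeterminates and leaves this row out, and item h of SAP 5.4.3 separately plots PPA over the full range of assumptions about indeterminates. This stands.

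The third reply is that shares of 10% or more have no support in the documents and are hard to reach under the ASIS rules after repeat testing. This stands too, although failures that are correlated between assays could raise the indeterminate rate above the enumerated figures.

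**Conclusion.** The point holds as a small gap in one sensitivity row. Following the SAP as written would put a binomial interval on partly modelled counts, and nothing in the plan carries the uncertainty of the modelling.

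The direction is certain and the size is conditional: negligible at 1–2% each of indeterminate and equivocal results, small at 5% each, material at 10% each, and worse with single assignment than with weighting. These figures assume results missing completely at random, the stated prevalence, and PPA and NPA of 96% and 99%. For Table 14 the effect is probably negligible.

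Two wider readings are not supported. The primary PPA and NPA, and the other scenarios, are fixed counts of observed cells with no modelled result in them. Nor does the interval shrink as more results go missing: the completed total stays about the same, so the interval fails to widen.

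**What to change.** In footnote 2 of Tables 12 and 14, state that the Score interval is not applied to the completed counts in this row, and name one of the following for both PPA and NPA:

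- multiple imputation, for example with 50 or more draws, combined by Rubin's rules on the logit scale; or
- a bootstrap over participants that refits the model and repeats the assignment or weighting in each resample.

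Name the model and its covariates in the same place. Say what will be done if a completed table has no disagreements, since the logit is then undefined; this is plausible for pharyngeal CT, which SAP 5.3.1 expects to be rare. Keep the Score interval for every row built on observed counts.

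The cost is a few lines of SAP text, minor programming, and a slightly wider interval in this one row. Data collection and the primary results do not change.
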